Vitamin D has been shown as an important marker of prognosis in a variety of clinical settings, including overall mortality, acute respiratory distress syndrome (ARDS), infection/sepsis, asthma, cardiovascular disease, diabetes, and pediatric/medical/surgical intensive care unit outcomes. Vitamin D not only plays a role in bone maintenance, but also a variety of extra-axial functions including immune-dysregulation and systemic inflammation. In addition, a number of randomized clinical trials support the supplementation of vitamin D as improving outcome in critical care patients. While the evaluation of vitamin D levels remains a standard-of-care at our institution, the widespread use of vitamin D monitoring and impact on neurocritical care patients remains limited. Our recent prospective observational study of vitamin D levels in neurocritical patients showed that deficiency (<20ng/ml) was highly associated with prolonged hospital stay and increased in-hospital mortality for emergent patients. Moreover, a number of limitations arise from this study due to its observational nature. **This study proposes a randomized, double-blinded, placebo-controlled, single center evaluation of vitamin D supplementation in the neurocritical care patient population (Table 1). Patients admitted to the neurocritical care unit for emergent cases and with vitamin D deficiency (<20ng/ml) will undergo vitamin D serum draw on admission and be randomized to receive cholecalciferol/vitamin D3 supplementation (540,000 IU once orally) or placebo with the primary measured outcome being hospital length-of-stay.** Secondary outcomes will include length of hospital course, length of ICU course, complications, adverse events, discharge Glasgow Outcome Score, in-hospital and 30-day mortality, as well as quality-of-life. Power analysis estimates 198 patients will be needed for each subgroup to determine a 2 day difference in length-of-stay, and we plan to recruit 218 patients per treatment arm to account for dropout, which will take approximately 6-9 months to recruit. Interim analysis and safety monitoring will be performed. We hypothesize that vitamin D supplementation may make a significant impact on reducing morbidity and mortality in the neurocritical care population. The possibility of reducing hospital length of stay and mortality from a simple and cheap intervention such as vitamin D supplementation may be a useful adjuvant treatment in the neurocritical care population.

2. Background/Rationale

Hypovitaminosis D has a high prevalence among the general population, with some studies showing over half of the elderly population being affected (Chapuy 1997). Among critically ill patients, various studies have shown associations between hypovitaminosis D and multiple negative outcomes including mortality (De Haan 2014,

Rech 2014), ARDS (Dancer 2015), and infection (Flynn 2012). Vitamin D deficiency has also been shown to have impacts on various neurological diseases such as stroke (Yalbuздag 2015, Chung 2015), and dementia (Littlejohns 2014). While the mechanism between vitamin D deficiency and these diseases is not entirely known, evidence suggest that vitamin D can affect vascular reactivity, inflammation, and the immune system (Carthy 1989, Vargas-Vasserot 2011) (Table S1, Figure S1-2).

Vitamin D has been shown to impact prognosis in a variety of retrospective and randomized clinical trials within an intensive care unit (ICU) environment (Amrein 2011). **Despite these findings, there have been no studies examining the impact of hypovitaminosis D in specialized neurocritical care units (NCCU).** Given the often significant differences in the management of patients in NCCU and more generalized intensive care units (Kurtz 2011) there is a need for further inquiries into the impact of low vitamin D levels in this specific environment. **This study proposes a randomized, double-blinded, placebo-controlled, single center evaluation of vitamin D supplementation in the emergent NCCU patient population (Table 1).** We have previously conducted a prospective, observational analysis of 823 NCCU patients and shown a significant reduction in hospital length-of-stay for all patients (7.14 vs. 5.97 days, $p=0.0018$) and for emergent cases (8.21 vs. 6.36 days, $p=0.038$), as well as reduced in-hospital mortality for emergent patients with non-deficient vitamin D levels (26/203 vs. 22/321, $p=0.021$). Nevertheless, these results remain limited in being observational studies without randomization or controls.

3. Study purposes and objectives

1. Evaluate the impact of vitamin D supplementation on the length-of-stay of emergent neurocritical care patients (primary outcome)
2. Evaluate the impact of vitamin D supplementation on in-hospital mortality, ICU length-of-stay, Glasgow Outcome Score on discharge, complications, and quality-of-life metrics (secondary outcome)
3. Evaluate the impact of vitamin D supplementation on Glasgow Outcome score and quality-of-life metrics at 3 and 6 months post-discharge (secondary outcome)

4. Methods

4.1. Inclusion criteria

- Patients >18 years of age
- Patients admitted to the neurosurgery or neurology services
- Patients admitted to a critical care unit
- Informed consent
- Expected to stay in the ICU for 48 hours or more
- Vitamin D deficiency (<20ng/ml)

4.2. Exclusion criteria

- Patients where a vitamin D level was not drawn within 48 hours of admission
- Patients not randomized within 48 hours of admission
- Readmitted patients to the critical care unit
- Lack of informed consent

- Prior supplementation with vitamin D
- Severely impaired gastrointestinal function
- Other trial participation
- Pregnant or lactating women
- Hypercalcemia (total calcium of >10.6 mg/dL or ionized serum calcium of >5.4 mg/dL)
- Tuberculosis history or clinical exam
- Sarcoidosis history or clinical exam
- Nephrolithiasis within the prior year
- Patients not deemed suitable for study participation (ie, psychiatric disease, living remotely from the clinic, or prisoner status)
- Pregnant or nursing women

4.3. General protocol

1. Patients will be identified through primary treatment teams, including the Departments of Neurosurgery and Neurology, and through screening of the electronic medical record for patients admitted to the NCCU at the University of Utah Health Sciences Center. Patients admitted for non-elective indications as outlined in the inclusion criteria will be enrolled. The full inclusion and exclusion criteria are listed in Table 1. We expect most patients to be admitted to the neurosurgery service and NCCU.
2. A Vitamin D level will be drawn on all non-electively admitted NCCU patients as part of our standard admission protocol.
3. Patients with a Vitamin D level <20ng/ml, defined as deficient, will be consented for the trial. Patients that do not consent for the trial will be studied retrospectively as part of our standard-of-care similarly to our previous prospective trial. Women between 18-45 years of age will undergo a serum or urine pregnancy test to rule out pregnancy prior to enrollment.
4. Patients will be randomized 1:1 to receive Cholecalciferol (Vitamin D3, 540,000 IU once orally or by feeding) immediately or placebo by random number generator. Treatments will be blinded to the patient and physician care teams. Placebos will include similar tablets or liquid formulations that mimic the treatment drug but are indistinguishable.
5. A subsequent Vitamin D level will be drawn 3 days after drug administration or on date of discharge if sooner than 3 days to evaluate the adequacy of vitamin D repletion.
6. Primary outcomes will total hospital length-of-stay. Secondary outcomes will include in-hospital mortality, ICU length-of-stay, ICU complications (rates of sepsis/bacteremia, pneumonia, urinary tract infection), discharge Glasgow Outcome Score, medication adverse events, and quality-of-life metrics. Various patient demographic data will be acquired.
7. Subsequent 30-day mortality will be measured on standard clinical follow-up.

8. 1, 3 month and 6 month Glasgow Outcome Scores and quality-of-life metrics will be obtained. Physical therapy gait distance measurements as well as modified Rankin scale on discharge will be obtained.

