4.4. Safety monitoring

There are minimal risks related to the patient. Vitamin D treatment is a relatively safe procedure in properly selected individuals. There may be additional discomforts including close monitored by the research team in order to monitor the study and collect data. The risk and side effects for Vitamin D administration are minimal and discussed further in the drug description. We have outlined a detailed data and safety monitoring plan.

We have previously shown Vitamin D administration in our prospective, observational study for patients with Vitamin D levels <10ng/ml to be safe and without any adverse effect at dosages of 50,000 IU Qweek of ergocalciferol/vitamin D2. The dosages used in this study are comparable to other studies evaluating Vitamin D efficacy and safety (Bacon 2009, Von Restorff 2009, Amrein 2011, Amrein 2014). There was no reported adverse event from ergocalciferol/vitamin D2 administration during our prospective, observational trial along with recent trials evaluating cholecalciferol/vitamin D3.

For patient safety, we will continue daily monitoring of CBC, BMP, Calcium, Phosphate, and neurological examinations as per standard practice in the neurocritical care unit. Should risks be identified, modification of the protocol will be proposed. And should the trial prove unsafe, we plan to notify the IRB and terminate the study. The study principal investigator and co-investigators will be responsible for oversight of patient safety. In addition, an independent safety and data review committee of licensed physicians will evaluate the study data on a quarterly basis. Quarterly safety and data monitoring reports will be discussed among the investigators and safety committee. The study will remain double-blinded except in the case of possible safety issues warranting unblinding.

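### The post-dose vitamin D level is informative about arm, and no step keeps the result from the blinded patients and care teams

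*Combined protocol and SAP*

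**What the plan says.** Section 4.3 item 4 states "Treatments will be blinded to the patient and physician care teams" and provides an indistinguishable placebo. Section 4.4 adds "The study will remain double-blinded except in the case of possible safety issues warranting unblinding".

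Item 5 of 4.3 orders the follow-up sample: "A subsequent Vitamin D level will be drawn 3 days after drug administration or on date of discharge if sooner than 3 days". Its stated purpose is to judge whether vitamin D has been repleted, and Table 2 lists the day-3 level among the clinical variables. Neither place says who receives the result or when.

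The nearest access statements lie elsewhere. Section 4.6 covers confidentiality and coding by study number. Section 4.7 limits access to stored study data to the principal investigator. Section 4.4 has quarterly safety and data reports discussed between the investigators and the safety committee. Table 1 adds a monthly data-entry review and a 6-month interim analysis. None of these governs what a laboratory reports to the chart.

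The level is not among the routine safety tests that 4.4 names: "we will continue daily monitoring of CBC, BMP, Calcium, Phosphate, and neurological examinations".

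**The concern.** The sample measures the pharmacological effect that separates the arms. An indistinguishable placebo cannot protect a blind if a result of this kind is open to the people who are meant to be blinded.

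The primary outcome is hospital length of stay, which depends partly on discharge decisions by the care team. ICU stay, discharge Glasgow Outcome Score and quality of life could also be affected by knowledge of the arm. Bias that enters through such decisions cannot be reliably removed in the analysis, so the protection has to sit in the conduct of the trial.

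**Working it through.** There is no figure in the plan to reproduce. The check has three parts: how informative the level is, whether it could be known before discharge, and what the two give together. All percentages below are illustrations. They show how well the level marks the arm and do not measure bias.

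**1. What the documents give**

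- Baseline below 20 ng/ml in every patient (4.1).
- Mean rise of 25 ng/mL in the treated group of a 25-patient pilot of this dose (Table S1). No time point is attached to that rise.
- Repletion of the majority by 2-7 days (4.8). This statement covers an intramuscular and the oral regimen together.
- An untreated cohort whose levels fell by 3 days after admission (Table S1), so a spontaneous rise on placebo is not expected.
- Pointing the other way, a suggested blunted response in the critically ill (4.8) and a trial of other doses in which levels peaked on day 5 (Table S1).

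Not given: the share at or above 20 ng/ml at day 3 in either arm, the SD of the change, and assay turnaround.

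**2. How well the level marks the arm**

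Let p and q be the shares of active and placebo patients at or above 20 ng/ml at the draw, with 1:1 allocation. A reader guesses active when the level is 20 or more.

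- Share of correct guesses = (p + 1 − q)/2. Chance is 50%.
- Share of high levels that come from the active arm = p/(p + q).

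| p | Correct, q = 0 | Correct, q = 0.10 | High levels from active, q = 0 to 0.10 |
|---|---|---|---|
| 0.30 | 65% | 60% | 100% to 75% |
| 0.51 | 75.5% | 70.5% | 100% to 83.6% |
| 0.65 | 82.5% | 77.5% | 100% to 86.7% |
| 0.80 | 90% | 85% | 100% to 88.9% |

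The value 0.51 stands for a bare majority. The value 0.65 is borrowed from a cited trial of other doses and another route, at 7 days. The values 0.30 and 0.80 and all values of q are assumptions.

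Cross-check with a normal model: correct guesses = Φ(rise/(2 × SD)), with no mean change on placebo and an assumed SD of change of 10, 15 or 20 ng/mL.

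- Rise of 25: 89.4%, 79.8%, 73.4%.
- Rise of 15 (assumed, a weaker response): 77.3%, 69.1%, 64.6%.

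**3. Whether the result could be known before discharge**

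Section 4.2 excludes "Patients not randomized within 48 hours of admission", and dosing is immediate. The day-3 draw therefore falls at about hospital day 0 + 3 = 3 to 2 + 3 = 5. With one day of turnaround (assumed), the result is available on day 4 to 6.

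The earlier study's mean stay in deficient emergent patients was 8.21 days (section 2). Entry requires "Expected to stay in the ICU for 48 hours or more", so I condition on a stay above 2 days. I used lognormal and gamma distributions with mean 8.21 and SD 6.1, 7.1, 8.2 or 10. The first two SDs are those implied by 198 per group and a 2-day difference at two-sided 0.05 with 90% and 80% power, since the plan states neither power nor SD. The other two are assumed.

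- P(stay > 4 | stay > 2) = 72% to 81%.
- P(stay > 5 | stay > 2) = 61% to 71%.
- P(stay > 6 | stay > 2) = 52% to 62%.

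Patients sampled on the day they leave are little affected.

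**4. Both together**

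If a fraction f of patients have a visible result before discharge with accuracy a, and the rest can only be guessed at chance, overall accuracy is 0.5 + f(a − 0.5). This treats stay and response as independent.

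- p = 0.51 to 0.80: from 0.5 + 0.52 × 0.205 = 61% to 0.5 + 0.81 × 0.40 = 82%.
- p = 0.30: from 0.5 + 0.52 × 0.10 = 55% to 0.5 + 0.81 × 0.15 = 62%.

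**The case against.** The strongest reply is that the plan is silent here and does not contradict itself. Section 4.4 already requires the blind to hold except for safety, so a general rule forbids revealing the arm and only an operational step is missing. The documents never say that the result reaches the care team. The opening summary calls vitamin D evaluation standard of care at the site, but 4.3 item 2 ties the standard draw to admission. The follow-up sample may therefore not follow the ordinary reporting route. This stands: the defect is a missing safeguard, and a reader who infers that the trial was in fact unblinded goes beyond the text.

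A reader might also infer that the level reveals the arm outright. It does not. Repletion is claimed for a majority only, the day-3 share is unknown, and a slow response brings the guess much closer to chance. That limits the force of the point without removing it, since a partial marker can still influence decisions.

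A third tempting reading is that the investigators treat the enrolled patients. They belong to the neurosurgery department (4.7), and 4.3 says "We expect most patients to be admitted to the neurosurgery service and NCCU". The documents do not say that they care for these patients or see this field, and the point does not rest on it.

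Finally, treating teams might want the level for safety. It is not among the daily tests named in 4.4. Those tests, committee review and safety unblinding can all continue with the level withheld.

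**Conclusion.** The concern holds as a gap in the blinding procedures. The plan promises that patients and care teams are blinded, orders a result that carries information about arm, and gives no step that keeps the two apart.

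The gap itself is certain from the text. Two things are not: whether the result would be released during the stay, and how much any release would matter. If it is visible, the level would mark the arm better than chance across the assumed range, from modestly (60% to 65% correct with 30% responding) to well (up to 90% with 80% responding). A majority of patients would probably still be in hospital when it arrives. No figure for bias in length of stay can be derived, and its direction is unknown.

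The change should be made because the safeguard is cheap and the primary outcome depends partly on the people who are to be blinded.

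**What to change.** Add to section 4.3 item 5, in substance: *The post-dose vitamin D result is withheld from patients, care teams, outcome assessors and blinded investigators until database lock, for example by being held in the laboratory or masked in the chart. The independent safety and data review committee keeps access, and the safety-unblinding route in 4.4 is unchanged.*

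Then reconcile this with three places by stating who sees this field: the investigators' safety oversight and quarterly reports in 4.4, the principal investigator's access to study data in 4.7, and the monthly data-entry review, quarterly independent review and 6-month interim analysis in Table 1. Database lock is a single release time that also covers the Glasgow Outcome Scores and quality-of-life measures taken after discharge.

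The cost is small: a laboratory or chart arrangement and a few matching sentences. The downside is that care teams do not routinely see the follow-up level during the stay. The field must also be entered or reviewed late, or by someone outside care and outcome scoring. Daily safety tests do not change, and no clinical rule is proposed.

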
• Name• Medical record number• Date of birth• Gender• Diagnosis• Ethnicity/race
Clinical Variables

• Date of admission to NCCU• Disease category (tumors, trauma, vascular, other)• Disease severity: Glasgow Coma Scale, Simplified Acute Physiology Score II• Medical comorbidities: diabetes, hypertension, heart disease, cancer history• Any surgeries during hospitalization• Randomization – vitamin D or placebo• Vitamin D level on admission• Date vitamin D level• Vitamin D level 3 days post treatment• Date vitamin D level 3 days post treatment• Date ICU discharge• Date hospital discharge• Date deceased• Glasgow Outcome Score on discharge• EQ-5D on discharge• Discharge disposition• Hospital complications (specifically: deep vein thrombosis, bacteremia, urinary tract infection, pneumonia, readmission to NCCU)• Glasgow Outcome Score at 3 and 6 months• EQ-5D at 1, 3 and 6 months• Physical therapy assessments at discharge• Modified Rankin Scale on discharge
Safety Monitoring

• Common Terminology Criteria for Adverse Events (CTAE) V4.0• Daily ICU laboratory studies (CBC, BMP, calcium, phosphate)• Daily neurological exam• Quarterly independent review of safety and data• Monitoring of adverse events

Table S1: Clinical Studies Evaluating Vitamin D in a Critical Care Environment			
Reference	Study type	Participants/ groups	Summary
Van den Berghe 2003	RCT	22 200 IU vs. 500IU	Minimal change in serum markers
Ostermann 2007	Retrospective cohort	100 Normal vs. insufficient vs. deficient	Hospital-free days were significantly different between patients with deficiency and sufficiency No significant relationship between 25(OH)D concentrations and mortality
Lucidarme 2010	Retrospective cohort	100 Normal vs. insufficient vs. deficient vs. undetectable	28-day mortality was significantly different between the four groups No significant association between 25(OH)D concentrations and length of ICU stay. 79% of patients had low 25(OH)D concentrations
Mata-Granados 2010	RCT	33 Placebo vs. 60,000 IU PO, vs. 2mcg IV vit D3	97% of critically ill patients were vitamin D deficient. Group B (60,000 IU) showed a statistically significant increase in 25(OH)D concentrations.
Cecchi 2011	Retrospective cohort	170 Severe sepsis vs. non-septic trauma	28-day mortality was not statically different between the two groups with rates of 27.9% in severe septic patients and 11.1% in trauma patients

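### Modified Rankin and gait distance are measured only at discharge, the day the treatment is meant to move; they have no reading at a common time, and the follow-up contacts lack a clear origin

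*Combined protocol and SAP*

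**What the plan says.** Section 4.3 item 8 sets the timing of the two functional measures: "Physical therapy gait distance measurements as well as modified Rankin scale on discharge will be obtained". Table 2 agrees, listing "Physical therapy assessments at discharge" and "Modified Rankin Scale on discharge". Neither measure has a later reading anywhere. Both were added as secondary outcomes by amendment 6.2 and stand under Secondary Aims in Table 1. GOS and EQ-5D also have a discharge reading in Table 2.

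The primary outcome is total hospital stay (section 4.3 item 6). The abstract sizes the trial "to determine a 2 day difference in length-of-stay".

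Follow-up of GOS and quality of life is described in three places:

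- Section 3, objective 3: "Glasgow Outcome score and quality-of-life metrics at 3 and 6 months post-discharge (secondary outcome". The origin is discharge, and there is no 1-month reading.
- Section 4.3 item 8: "1, 3 month and 6 month Glasgow Outcome Scores and quality-of-life metrics will be obtained". No origin is stated, and a 1-month GOS is included.
- Table 2: "Glasgow Outcome Score at 3 and 6 months", with EQ-5D at 1, 3 and 6 months. No origin is stated, and there is no 1-month GOS.

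Section 4.9 leaves the analysis of secondary outcomes to unspecified methods. It plans no adjustment for the time at which function was scored.

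**The concern.** An outcome scored at discharge is scored at a time that the trial expects to differ between arms. Two simple accounts of discharge show why this is hard to read.

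- If discharge is decided on grounds unrelated to function, patients with a shorter stay are scored earlier in recovery. The arm with the shorter stay can then look worse without any true functional difference.
- If patients leave once they reach a certain functional level, the arms look alike at discharge even when one arm recovered faster.

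After a positive primary result, the first question will be whether the shorter stay came with equal, better or worse function. Modified Rankin and gait distance, as planned, cannot answer it. A fixed-time score that was not collected cannot be recovered later.

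The origin of the follow-up contacts is a smaller matter of the same kind. A clock that starts at discharge starts on a day that treatment may change, and it never starts for a patient who dies in hospital.

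**Working it through.** **Inputs.** Planned effect: 2 days (abstract). Mean stay of deficient emergent pilot patients: 8.21 days, against 6.36 in non-deficient patients (section 2). In-hospital deaths among the deficient: 26/203 (section 2). Group size: 198, or 218 with dropout (section 4.9). Assumption: months are taken as 30, 90 and 180 days.

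**The plan's own figures.** The pilot difference is 8.21 − 6.36 = 1.85 days, close to the planned 2. The figure 218 is 198 × 1.10 = 217.8, rounded up. The figure 198 cannot be rebuilt, because SD, power and sidedness are not given; this point uses only the 2-day effect.

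**Step 1: shift in assessment time.** With stays of 8.21 and 8.21 − 2 = 6.21 days, and contacts counted from discharge, the relative shift is 2 / (8.21 + follow-up days):

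| Reading | Calculation | Shift |
|---|---|---|
| Discharge | 2 / 8.21 | 24.4% |
| 1 month | 2 / 38.21 | 5.2% |
| 3 months | 2 / 98.21 | 2.0% |
| 6 months | 2 / 188.21 | 1.1% |

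Counted from randomisation, the shift is zero at every contact.

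The discharge share depends on the mean stay. Randomisation may fall up to 48 hours after admission (section 4.2), so at that limit the share of time since randomisation is 2 / (8.21 − 2) = 32%. At the 20.1-day stay that Table S1 shows for the 475-patient randomised trial, it is 2 / 20.1 = 10%.

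**Step 2: what such a shift could do.** The documents hold no functional recovery data, so this step is an illustration on assumed curves. Assume no true effect on function, discharge unrelated to function, total recovery of 1 SD, and a recovered fraction f(t) = 1 − exp(−t/τ). The spurious difference is b = f(8.21 + m) − f(6.21 + m), in SD units, with m the follow-up days. Its standard error with 198 per arm is √(2/198) = 0.1005. The two-sided rejection rate is Φ(b/SE − 1.96) + Φ(−b/SE − 1.96), against a nominal 5%.

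| τ (days) | b at discharge | Rejection | b at 1 month | Rejection |
|---|---|---|---|---|
| 7 | 0.102 | 17.5% | 0.001 | 5.0% |
| 14 | 0.085 | 13.6% | 0.010 | 5.1% |
| 30 | 0.052 | 8.2% | 0.019 | 5.4% |
| 60 | 0.030 | 6.0% | 0.018 | 5.4% |

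At 3 and 6 months b is at most 0.007 and 0.001 SD, and rejection stays at 5.0%. With total recovery of 0.5 SD, b at discharge is 0.015 to 0.051 and rejection is 5.2% to 8.0%.

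If patients instead leave on reaching a functional level, the discharge difference is zero by construction, whatever the speed of recovery. The two accounts give different answers, and the documents do not say which is closer to practice.

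**Step 3: in-hospital deaths.** 26/203 = 12.8%. At that rate, 0.128 × 218 = 27.9, or about 28 patients in an arm, would have no discharge from which to count a contact.

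**The case against.** Much can be said for the plan.

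- **Follow-up readings exist.** A reader might infer that all functional outcomes are timed by the primary outcome and none can be compared fairly. The documents do not support that. At 3 and 6 months the shift is about 2% and 1% of elapsed time, so GOS and EQ-5D there are close to fixed-time readings. They largely answer whether earlier discharge came with worse function. This stands. What it leaves open is Rankin and gait distance, which have no such reading.
- **The direction is not known.** A reader might infer that a true benefit on stay would bias the discharge scores against vitamin D by a definite amount. That requires discharge to be unrelated to function and treatment not to speed recovery. The documents establish neither. A 2-day difference in means may also come from a few long stays and need not mean that patients in general are scored 2 days earlier. This stands too.
- **Discharge status is a legitimate comparison.** It is well defined, and objective 2 prespecifies discharge GOS. This is accepted: nothing here calls for removing or demoting the discharge scores.
- **Deaths are not lost.** Date of death is recorded, and in-hospital mortality is its own outcome. True, but that does not say how these patients enter a GOS comparison counted from discharge.
- **These are late-added secondary outcomes.** The primary analysis and sample size are unaffected. This limits the weight of the point but does not remove it, since the remedy is cheap.

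**Conclusion.** The point holds for modified Rankin and gait distance. Both are scored only on a day that the treatment is meant to change, by a planned 2 days or about 24% of the pilot mean stay. If stay differs between arms, these scores mix function with time since randomisation. The 24% assumes that the pilot mean of 8.21 days carries over to the trial. The resulting bias in the scores has no known direction or size; the illustrative 0.03 to 0.10 SD rests wholly on assumed recovery curves and on discharge being unrelated to function.

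For follow-up GOS and EQ-5D the defect is one of specification, not material timing bias. Only objective 3 names discharge as the origin, and only for 3 and 6 months. The 1-month contact has no origin, the 1-month GOS appears in one place of three, and a discharge origin is undefined for patients who die in hospital. This is worth correcting as an inexpensive improvement; it does not threaten the primary outcome.

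**What to change.** In section 4.3 item 8, objective 3 and Table 2:

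1. Count the 1-, 3- and 6-month contacts from randomisation, at days 30, 90 and 180, each with a stated window.
2. Score modified Rankin at those contacts, alongside GOS and EQ-5D.
3. Give the same GOS time points in all three places.

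Keep the discharge scores as planned. Report them with the day of assessment, which can be derived from the admission and discharge dates already in Table 2 once the randomisation date is recorded. Interpret them as status at discharge rather than recovery at a common time. This applies to gait distance in particular, which gains no fixed-time reading from this change.

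The cost is protocol wording and a few minutes at contacts already planned. The downside is that some patients still in hospital at day 30 will be scored as inpatients.
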